1.0 Objectives*

1.1 Describe the purpose, specific aims, or objectives.

The purpose of the data collected through this project is to investigate the comparative effectiveness of two evidence-based models for creating program cultural competency in diabetes self-management programming. We will compare two diabetes self-management programs that serve a large low-income Latino population and that employ different evidence-based models of culturally competent health promotion. *A priori*, we believe patient populations for each program will be similar, yet we will compare sample characteristics and assess treatment differences after adjusting for possible population differences within our statistical models to mitigate self-selection bias and possible confounding. We will use a quasi-experimental design with an embedded, mixed-method approach.

[figure not shown]
Specific Aims:

*Aim #1: Characterize the ways that two culturally competent diabetes self-management programs **interface** with patient culture and socioeconomic context*

*Aim #2: Measure and compare improvement in patient **capacity** for diabetes self-management*

*Aim #3: Measure and compare patient **success** at self-management*

1.2 State the hypotheses to be tested.

The hypothesis of our study is that diabetes self-management programs are most successful if their design is culturally and contextually “situated.”³⁶⁻³⁸ Trickett proposes that cultural competence entails integrating components of an intervention “into the local expression of culture as reflected in the multiple levels of the ecological context.”³⁸ Rather than merely “tailoring” an existing intervention to target a specific context or population (for example, by offering recipes for healthy meals using Latino cuisine or providing educational materials in Spanish), he emphasizes the need for interventions to be “situated” to fit synergistically within broader community dynamics (culture and socio-

economic context). Following Trickett, and reflecting input from our patient partners, we believe that getting people to adopt lifestyle and behavior changes outlined in guidelines for diabetes self-management requires positively leveraging the cultural values and accommodating the socio-economic circumstances of a patient population in a way that creates synergy with specific social dynamics that define patients' everyday lives.^{22-29,32,33}

2.0 **Background***

2.1 *Describe the relevant prior experience and gaps in current knowledge.*

The Specter of Uncontrolled Diabetes. Diabetes is among the Institute of Medicine's top 25 national priorities for Comparative Effectiveness Research (CER).¹ Twenty-nine million people or 9.3% of the U.S. population have type 2 diabetes.² If trends continue, one third of U.S. adults will develop diabetes by 2050.² While statistics this large can seem remote and impersonal, the patient members of our project team can put a human face on the numbers. Each of them has life-altering personal experience with diabetes. Not only do they have diabetes or pre-diabetes themselves, they also have family members or *multiple* family members with diabetes. Grimly, because uncontrolled diabetes is widespread among Latinos from low-income households, our patient team members have witnessed the terrible consequences of the disease: death, amputations, blindness, debilitating depression, and shattered lives. They report that diabetes is so common in the Latino community that people just *assume that they will get it*, and if they are diagnosed with diabetes, given what they have seen happen to their family and friends, *they believe that diabetes is a death sentence about which there is nothing that they can do*. So most of the time, *they do nothing*. As researchers, we were starkly confronted by this reality when two individuals affiliated with our preliminary patient-engaged research project died one month apart from complications of uncontrolled diabetes. These deaths were deeply disturbing and underscored the gravity of our work to understand the most effective way to help people develop the skills for diabetes self-care. Our patient team members fear diabetes not only for themselves and their adult family members, but also for the future that awaits their children growing up with the specter of diabetes but without the knowledge, capacity, or skills to take control of their own health destiny. Our proposed project seeks to disrupt this fatalistic dynamic of despair. As such, our partners, who are Latino patients from low-income households, their family members, and healthcare providers who serve this population of patients recognize effective diabetes self-management as a matter of life-and-death.

Diabetes Health Disparities. Although diabetes is a national health crisis, risk is not the same for everybody. Individuals from minority and ethnic

PROTOCOL TITLE: Comparing Program Options for Latinos with Diabetes

populations and those with low-income status are at significantly higher risk.³ This disparity brings the life-and-death reality of diabetes discussed in the preceding section even more negatively into relief. For example, Latinos are more likely (12.8%) than non-Hispanic whites (7.6%) to be diagnosed with diabetes,² and Latino youth have the fastest growing rate of diabetes.⁴ According to an analysis of data from the U.S. National Longitudinal Mortality Study, Latinos are also 28% more likely to *die* from diabetes, with Mexican Americans (representing 33.5 million people or 64.6% of U.S. Latinos and the overwhelming majority of the patients associated with the proposed research)⁵ 50% *more at risk*.⁶ Not surprisingly, a recent national poll by Harvard, NPR, and the Robert Wood Johnson Foundation found that diabetes is the top health concern for Latino families.⁷ Similarly, poverty has an impact on diabetes risk. Research shows that individuals from low-income communities experience higher rates of diabetes.⁸⁻¹¹ Analysis of National Health Interview Survey data found that *the* “greatest disparities [for diabetes risk] were experienced by the groups who had the lowest level of education, were living below the Federal Poverty Level (FPL), or both.”³ This is a troubling concern for Latinos given the high level of Latino poverty (23.2%).¹² In New Mexico, where Latinos make up 47% of the population,¹³ ethnicity and poverty both play a significant role in diabetes health and health disparities. For Latinos, rates for diabetes diagnoses (11.9%) and the diabetes death rate (45.9 per 100,000) are both more than twice those for non-Hispanic whites (5.3% and 22.5).^{14,15} Similarly, New Mexico is the second-poorest state in the nation after Mississippi, with poverty among Latinos (24% for 18-64 year-olds and 37% for 17-and-under) significantly higher than among non-Hispanic whites (12% and 13%).¹⁶ Individuals in New Mexico from low-income households are nearly three times more likely to be diagnosed with diabetes (14%) than individuals from households making more than \$50,000 (5.2%),¹⁷ meaning that given the Latino poverty rate, diabetes risk for individuals from low-income Latino households is disproportionately high.

Gaps in Evidence Related to Health Promotion Models for Diabetes Self-Management. Biomedical approaches to diabetes care are well-established, but pharmacologic therapies are often extremely costly, may have problematic health side effects, do not always result in the intended improvement in patients’ diabetes health, and regimens are not always easy to follow given social and environmental barriers faced by low-income patients. Instead, health guidelines emphasize the important role of patient self-care over narrow reliance on medical treatments for reducing the health impact of diabetes and improving diabetes health outcomes. The *Guide to Community Preventive Services* instructs individuals to engage in lifestyle changes based on combined diet and physical activity improvements as the best way to prevent and manage type 2 diabetes.¹⁸ The *Michigan Quality Improvement Consortium Guidelines for Management of Diabetes Mellitus* recommend that

PROTOCOL TITLE: Comparing Program Options for Latinos with Diabetes

individuals be given “comprehensive diabetes self-management education.”¹⁹ *Recommended Lifestyle and Self-management Guidelines from the American Diabetes Association* discuss the importance of individualized education, monitoring, and counseling.²⁰ We know how individuals can self-manage their diabetes or prevent pre-diabetes from becoming full diabetes – patient self-care through daily physical activity, a healthy diet, minimizing stress, and for those with full diabetes, regular glucose self-monitoring.²¹ But these are not things that can happen in the clinic or via prescription; they are things that the patient must do to care for him- or herself every day. The various guidelines tell us what needs to happen, but diabetes health outcomes are not improving.² The guidelines do not provide a roadmap for getting individuals to embrace necessary self-care practices. However, *systematic reviews* have repeatedly demonstrated that culturally competent health promotion approaches that account for culture and the social context of poverty can be key to improving health outcomes.²²⁻³¹ In particular, culturally competent self-management interventions have been shown to significantly improve both glycemic control and behaviors related to diet and physical activity, and also to increase diabetes-related knowledge. As a result, “*cultural competence*” has become a buzz phrase in diabetes health promotion. A variety of different models have been developed to create “*culturally competent*” diabetes self-management programming.²²⁻³¹ Yet, there is no agreement on what cultural competence actually means or entails, and because of a continued emphasis on individual behavior in approaches to diabetes health promotion, the design of self-management programs does not always create cultural competence in a way that makes sense in relation to patients’ lives or improves their health.

2.2 *Describe any relevant preliminary data.*

How We Selected Appropriate Interventions and Comparators.

We are collaborating on this project with two diabetes programs in Albuquerque. We selected these programs as comparators because they represent distinct evidence-based models for culturally competent diabetes self-management programming. We chose two sites implementing these models that actively serve a large number of Latino diabetes patients from low-income households in Albuquerque, New Mexico. Following Trickett,^{37,38} we believe that the program model that interfaces most synergistically with patient’s culture and everyday life circumstances will have the best diabetes health outcomes.

Comparator #1.

The Diabetes Self-Management Support Empowerment Model (DSMS).⁴¹ The Center for Diabetes Education at the University of New Mexico Hospital (CDE-UNMH) bases its program on the Diabetes Self-Management Support Empowerment Model (DSMS).⁴¹ The CDE-UNMH follows National Standards for Diabetes Self-Management Education,²⁰ is certified by American Diabetes Association,⁴² and is accredited by the American Association of Diabetes Educators (AADE).⁴³ The DSMS

PROTOCOL TITLE: Comparing Program Options for Latinos with Diabetes

Framework: The DSMS is a patient-centered, theoretically based educational framework. The DSMS combines a series of clinically informed group didactic sessions that use a patient self-determination approach to empower patients to take control of their own diabetes health with follow-up supports to sustain self-management gains achieved during the sessions. The AADE requires that educators acquire proficiency in culturally competent supportive care across the lifespan as one of five domains for certification so that educators can be informed about and aware of specific challenges that might accrue in the patient's diabetes self-management experience. This program represents the gold standard for diabetes self-management education focusing on changing eating and physical activity behaviors, self-monitoring, risk reduction, and stress management.

Implementation of the DSMS at CDE-UNMH: The CDE-UNMH program uses the DSMS group education approach. Patients attend a six-week group instructional session with nine hours of class plus a one-on-one follow-up with a certified diabetes educator to provide individualized support by creating a customized education plan. The group sessions have discussion supported by didactic conversation "maps" where the facilitator guides but does not control the conversation based on session thematic goals. Patients then complete self-assessment forms. This format is the foundation of the DSMS Model for creating patient empowerment and program cultural competence.

Comparator #2.

The Chronic Care Model (CCM).^{31,44} The One Hope Centro de Vida Health Center Diabetes Program (One Hope) is based on the Chronic Care Model (CCM).^{31,44} The Chronic Care Model Framework: The CCM is "a systematic approach to restructuring medical care to create partnerships between health systems and communities"⁴⁴ by addressing not only the medical but also the cultural and linguistic needs of patients through the inclusion of cultural competence in the delivery system design.³¹ The CCM involves six synergistic domains: 1.) Improved access to care, 2.) Patient self-management support, 3.) Patient decision support, 4.) Care coordination, 5.) Integrated health information systems, and 6.) Access to community resources. The use of the CCM framework has been shown to yield significant results in the treatment of diabetes and is being used widely in chronic disease management.⁴⁵ To create a holistic care regime, the CCM focuses on addressing social determinants of health by meeting the medical, cultural, and linguistic needs of patients through integration of cultural norms and social relationships from the patient population into program design.³¹

Implementation of the CCM at One Hope: The One Hope program is designed to address the specific needs of Latino patients from low-income households^{32,33} by creating comprehensive, integrated, wrap-around services focused on culturally competent care.^{31,44} One Hope emphasizes Spanish as the language for service provision³³ and access to care

PROTOCOL TITLE: Comparing Program Options for Latinos with Diabetes

regardless of ability to pay. The One Hope facility provides a physical environment that reflects the lifestyle and economic capacity of patients to make them feel comfortable and that they “belong” (in contrast to more clinical, corporate, or academic medical settings). One Hope is a community-run clinic with a director and staff who are members of the community and who are culturally and economically similar to the patients they serve, reducing the hierarchical power relationship that generally exists between patients and providers. This approach is evident in the way that doctors at One Hope share decision-making by engaging the patient and their family members in creating a plan for diabetes self-management.^{46,47} In addition, patients, caregivers and family members participate in a variety of program activities including cooking and nutrition workshops, zumba classes, and citas compartidas sessions (“shared appointments”).^{30,47-49} These shared appointment sessions allow patients, social supports and family members to share their stories and experiences in a peer support setting with facilitation by medically trained providers. But providers also “co-learn” from the patients.^{27,35,36} Through shared decision-making and shared appointments, providers learn about the realities of patients’ lives and their daily struggles at a level that goes beyond the interaction that normally occurs in a clinic. This helps the provider to be culturally competent by understanding diabetes from the perspective of the patient. Sharing experiences with peers and providers and including family members in activities offers a different level of social support for the patient by creating an enhanced feeling of intimacy and inclusion within the program. Innovative salidas (exit interviews), conducted routinely with all patients by a bilingual health navigator ensures that the patient understands and feels capable of implementing a doctor’s instructions, and integrates health system information by allowing the health navigator to communicate details of patient status back to the provider.³²

Using the CCM model, One Hope has had many patients improve their health, including individuals who have been able to reduce or stop taking their diabetes medication. One Hope staff note that people participating in the diabetes program have changed their food- and physical activity-related behaviors and attitudes. Lowered blood sugar levels and improved diabetes self-maintenance have been reported anecdotally. One Hope conducted a preliminary analysis of patient medical records and found that CCM diabetes patients demonstrated statistically significant decreases in A1c values at months #5, 8, 11, 14, 18 and 22 after they joined One Hope’s program.¹⁰²

Our comparator choice will reduce the potential for biases and allow for direct comparisons. The two comparator sites are distinct in their diabetes management program models, thus allowing (after controlling for other factors) for direct comparison of the effects of the program on the primary and secondary outcomes. This choice of comparators will

PROTOCOL TITLE: Comparing Program Options for Latinos with Diabetes

reduce the potential for bias for the following reasons: 1.) The two comparators serve relatively similar populations in terms of socio-demographic attributes. 2.) Diabetes self-management program models in use at the two comparator sites have program attributes that are sufficiently distinct to allow contrast and comparison. And, 3.) Each of the comparator sites is implementing a program in a “real life” setting, thus providing the opportunity for a pragmatic assessment of the comparative effectiveness of the program models under externally valid and generalizable conditions.

2.3 Provide the scientific or scholarly background for, rationale for, and significance of the research based on the existing literature and how will it add to existing knowledge.

Different models are being used to make diabetes self-management programs culturally competent. However, this variation creates uncertainty for a patient with diabetes who does not understand that programs can differ significantly, how they differ, or which programs offer them the best option. For Latino patients from low-income households, it is not clear which type of culturally competent self-management programming most effectively integrates their culture and accommodates their socio-economic circumstances in a way to best improve their diabetes health. The proposed research will help to fill this gap by using patient-identified issues of importance as measures for directly comparing different evidence-based models for culturally competent diabetes self-management health promotion being implemented by programs that are currently available to Latino patients from low-income households in Albuquerque, New Mexico. PCORI supported us to develop this application through two “pipeline” awards (Tier I 2014 & Tier II 2015) to engage our patient stakeholders in conceptualizing CER to investigate *“Culturally Appropriate Options for Diabetes Prevention and Care for Low-Income Latinos.”* Outside of our Tier I and Tier II projects, the cultural and contextual framework for research that we present here has not previously received PCORI funding. This framework aligns with PCORI’s interest in inclusiveness for under-served minorities. Our patient-engaged preliminary research and the work of our PCORI Tier projects suggests that the proposed project will offer significant benefit to patients trying to find support for developing the knowledge and capacity to self-manage their diabetes.^{32,33} Our Patient Advisors recognize the imperative of everyday diabetes self-care strategies. But the reality is that too many lack the skills to leave behind fatalistic attitudes regarding diabetes as their destiny and they have no way to develop the knowledge and capacity to successfully adopt the changes outlined in the guidelines, improve their Hemoglobin A1c (glycosylated hemoglobin), or successfully control their diabetes. Improving models and approaches for diabetes self-care health promotion is critical to the health of our Advisors, their adult family members, and their children. The results of this research have

PROTOCOL TITLE: Comparing Program Options for Latinos with Diabetes

implications for other Latino populations, for other minority patients, and for models for self-management for other chronic conditions.

How the Research is Focused on Questions that Affect Outcomes of Interest to Diabetes Patients and their Caregivers.

"I have diabetes, but I am not just a patient. I am a person. I have cultural values and concrete realities that shape my everyday life. Both need to be considered for me to be able to feel that my care is making me well and to make it more likely that I can control my A1c. With this in mind, which of two self-management programs is the most culturally and contextually appropriate option for me to take the best care of myself in relation to my diabetes?"^[Translation from Spanish]

We co-developed this research question with a 10-member Patient Advisory Board of patients, social supports and researchers through our PCORI Tier I and II awards. Diabetes has been identified by our patient partners as a health issue of extreme urgency. Specifically, they are concerned about the failure of diabetes self-management programming to account for important dimensions of Latino culture or the social context created by poverty. At our PCORI Tier I Patient Advisory Board meetings, patients and social supports discussed these issues with us extensively and with emotion. What they had to say supported what we heard in previous conversations with patients and community members, and in our preliminary research.^{32,33} Patients, social supports and community members report: a.) A lack of cultural competence on the part of providers, b.) A lack of programming in Spanish, c.) Failure of program design to understand or accommodate the dynamics of Latino culture related to core values that prioritize both the importance of social relationships and the need to avoid personal conflict,^{34,35} d.) Poor program accommodation of the fact that patients lack resources,³⁶ and e.) A lack of attention to the extent to which poverty results in low diabetes health literacy, low capacity to deal with chronic disease, and high stress.³⁶ All of these factors influence patients' ability to comply with recommendations regarding drugs, diet, and physical activity to self-manage their diabetes. We will use the above question and patient-reported outcome measures to guide a mixed-method comparative study of the effectiveness of two models of diabetes self-management programming currently being used by programs that serve a large population of Latino patients from low-income households in Albuquerque, New Mexico. Each program employs a distinct evidence-based approach to create program cultural competence.

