We will create a database with all interview and focus group transcripts. We will conduct a theory-driven qualitative content analysis. We will read through transcripts to identify conceptual categories and patterns related to specified domains of inquiry, create a qualitative codebook, and develop conceptual summaries for each transcript. Following review and summary, we will code transcripts for systematic themes and sub-themes within the domains. We will explore interconnections between theme categories and develop a holistic interpretation of the data.

Statistical Analysis Aim 3. We will conduct analyses to assess successful patient management of their diabetes (Aim #3), our secondary outcomes, by measuring their A1c from blood samples drawn, BMI calculations, cortisol from hair samples, and PHQ-9 scores obtained at baseline, 3, 6, and 12 months. Clinical analysis of blood samples will use A1c tested on whole blood as described previously. Change in A1c over the four time points in each of the diabetes self-management program models will be evaluated by fitting a linear mixed model to A1c with the primary independent variable treatment site while adjusting for demographic covariates, social support and knowledge, the measures hair cortisol indicating stress levels, and participant and social support scores on the CAHPS-CC. An interaction between time and site will be included to explore how A1c scores change over time. For the secondary endpoint analysis, REML-adjusted least-squares mean estimates of change in A1c from baseline to 6 months post-intervention will be reported along with their 98.3% confidence intervals (the significance level includes a Bonferroni adjustment for three secondary outcomes). A model incorporating the 12 month time point will also be evaluated. BMI and depression scores will be analyzed similarly.

11.2 Provide a power analysis.

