- 1.) Hypothesis: The CCM model will result in a larger decrease in percent A1c from baseline to 6 months with Cohen's f ES = 0.06 as compared to the DSMS. Previously published studies and institutional experience evaluating culturally competent diabetes management programs report changes in percent A1c with effect sizes of 0.01 to 0.06 in studies ranging in sample size per arm from 26 to 133.^{66,105-107}
- 2.) Hypothesis: The CCM model will result in a larger decrease in BMI from baseline to 6 months than DSMS with a clinically meaningful difference of 1.5 kg/m² between the groups (Cohen's f ES = 0.06).^{67,68}
- 3.) Hypothesis: Compared to DSMS, CCM will result in a larger decrease (by 3 points) in PHQ-9 scores from baseline to 6 months (Cohen's f ES = 0.06).¹⁰⁷⁻¹⁰⁹

Note: It is coincidental that the effect sizes (and power) are the same for each of the three secondary outcomes

Power Calculations. We will recruit N=240 patient-social support pairs (n=120 per site) with anticipated 20% attrition to obtain complete data on at least n=96 per site. Comparing response changes on the DKQ, PAM-13, and DHQ-9 from baseline to 6 months between the CCM to the DSMS, the two-sided Type I error rate was adjusted for the number of comparisons made (four comparisons for the co-primary outcomes) using a Bonferroni correction ($\alpha=0.0125$). The power analyses for detecting site differences among change scores were based on multiple linear regression models including demographic characteristics, participants' perceived cultural competence of providers (CAHPS-CC), and social supports' change scores on the DHQ, PAM-13, and DHQ-9 as covariates. We report Cohen's f effect sizes based on the regression method.^{110,111}

The power for the primary endpoints with n=96 per site and $\alpha=0.025$ are as follows:

- 1.) Change in DKQ summed score: $\Delta_{CCM-DSCS} = 2.2$ (SD = 3.8), power = 96%, Cohen's f effect size (ES) = 0.09
- 2.) Change in PAM-13 raw score: $\Delta_{CCM-DSCS} = 12.7$ (SD = 24.8), power = 85%, Cohen's f ES = 0.07

The power for the secondary endpoints with n=96 per site and $\alpha=0.017$ for comparing the CCM to the DSMS:

- 1.) Change in A1c: $\Delta_{CCM-DSCS} = -0.5$ (SD = 1.0), power = 84%, Cohen's f ES=0.06.
- 2.) Change in BMI: $\Delta_{CCM-DSCS} = -1.5$ (SD = 3), power = 84%, Cohen's f ES=0.06.
- 3.) Change in depression scores (PHQ-9): $\Delta_{CCM-DSCS} = -3$ (SD = 6), power = 84% Cohen's f ES = 0.06.

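### Both programmes use group sessions, but no class or group term is specified, so the site standard error may be too small and the stated power somewhat high

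*Combined protocol and SAP*

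**What the plan says.** Section 2.2 describes how the programmes are delivered. At CDE-UNMH (DSMS), "Patients attend a six-week group instructional session with nine hours of class", with facilitated group discussion, and each patient also has an individual follow-up with an educator. At One Hope (CCM), "These shared appointment sessions allow patients, social supports and family members to share their stories and experiences in a peer support setting"; cooking workshops and exercise classes are offered too. Class or group size, number of classes and stability of membership are not stated for either site.

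Section 11.1 (Statistical Analysis Aim 3) plans to assess A1c by "fitting a linear mixed model to A1c with the primary independent variable treatment site", with a time-by-site interaction and covariates, and BMI and depression scores similarly. The random effects are not listed. No separate analysis model is written for DKQ and PAM-13. The nearest text is in section 11.2, where power is based on "multiple linear regression models including demographic characteristics", CAHPS-CC and the social supports' change scores.

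On sample size, section 11.2 recruits 120 patients per site "with anticipated 20% attrition to obtain complete data on at least n=96 per site". No ICC, design effect, class or facilitator term, or cluster-robust variance appears anywhere.

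**The concern.** Patients in one class share a facilitator, discussions and peers for six weeks. Knowledge and activation, the two co-primary outcomes, are what such shared exposure could plausibly move together. If gains correlate within class, 96 completers at CDE-UNMH carry less information about the site mean than 96 independent patients. An analysis that ignores this gives confidence intervals that are too narrow and a type I error above the Bonferroni level. The planned power is also overstated, and PAM-13 and the three secondary outcomes are stated at only 84% to 85% to begin with.

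**Working it through.** **Inputs from the documents (section 11.2).** n = 96 completers per site, two-sided tests. DKQ: difference 2.2, SD 3.8, stated power 96%. PAM-13: 12.7, SD 24.8, 85%. A1c: 0.5, SD 1.0, 84%. BMI (1.5, SD 3) and PHQ-9 (3, SD 6) have the same standardised difference of 0.5 and the same stated power. Alpha is 0.017 for secondary outcomes. For the primary outcomes the power text gives 0.0125, but the list is introduced by "The power for the primary endpoints with n=96 per site and $\alpha=0.025$ are as follows".

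**Step 1: reproduce the stated power under independence.** SE = SD × √(2/96); power ≈ Φ(difference/SE − z), with z the two-sided critical value.
- DKQ: SE 0.548, ratio 4.011. At alpha 0.025 (z = 2.241), power is 96.2%, matching 96%.
- PAM-13: SE 3.580, ratio 3.548. At alpha 0.0125 (z = 2.498), power is 85.3%, matching 85%. At 0.025 it is 90.4%, which does not match.
- A1c, BMI, PHQ-9: ratio 3.464. At alpha 0.017 (z = 2.387), power is 85.9%, within 2 points of 84%.
- Recruitment: 96/(1 − 0.20) = 120 per site, so the inflation covers attrition and nothing else.

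The shortfall of about 2 points in the secondary figures is not evidence of a clustering allowance. DKQ and PAM-13 reproduce without one.

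**Step 2: bound the study patients per class, m (assumption).** The recruitment table in section 21.0 shows 32 participants, or 16 pairs, a month. Split equally, that is 8 patients a month at CDE-UNMH, or 8 × 1.5 = 12 per six weeks. If only one class runs at a time and 20% drop out, m = 12 × 0.8 = 9.6 completers. The window in section 7.1 (months 3 to 22, 20 months) gives 120/20 = 6 a month, 9 per six weeks and 7.2 completers. Parallel classes would lower m. I use m = 3 to 9.6.

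**Step 3: the ICC (assumption).** The documents give none. I use 0.01 to 0.05.

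**Step 4: effect of clustering in the DSMS arm only.** Design effect DE = 1 + (m − 1) × ICC. The true SE is √((1 + DE)/2) times the independence SE. True type I error at nominal 0.025 is 2 × (1 − Φ(2.241/SE ratio)).

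| m, ICC | DE | SE ratio | Type I (nominal 0.025) | DKQ (0.025) | PAM-13 (0.0125) | A1c/BMI/PHQ-9 (0.017) |
|---|---|---|---|---|---|---|
| independence | 1 | 1 | 0.025 | 96.2% | 85.3% | 85.9% |
| 3, 0.01 | 1.02 | 1.005 | 0.026 | 96.0% | 84.9% | 85.6% |
| 6, 0.02 | 1.10 | 1.025 | 0.029 | 95.3% | 83.3% | 84.0% |
| 7.2, 0.05 | 1.31 | 1.075 | 0.037 | 93.2% | 78.9% | 79.9% |
| 9.6, 0.05 | 1.43 | 1.102 | 0.042 | 91.9% | 76.5% | 77.5% |

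**Step 5: two sensitivities at m = 6, ICC 0.02.**
- Same clustering in both arms: SE ratio √1.10 = 1.049; power 94.3% (DKQ), 81.2% (PAM-13), 82.0% (secondary).
- Few classes, DSMS arm only: 96/6 = 16 classes, so 15 degrees of freedom for that arm. Satterthwaite degrees of freedom = (1.10 + 1)²/(1.10²/15 + 1²/95) ≈ 48. Power is then 94.2%, 80.3% and 81.4%.

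**The case against.** **Independence is partly inferred.** No analysis model is written for DKQ and PAM-13, and the random effects of the A1c model are not listed. This stands: the accurate statement is that no class term is specified. The power calculation itself is independence-based, because its figures reproduce that way.

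**The size is assumed.** Neither m nor the ICC has a source in the documents. An ICC for knowledge need not carry over to A1c or BMI at 6 months, well after a six-week class has ended. At the low end the effect is negligible. This stands too, so only a range can be given.

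**Stronger readings the documents do not support.**
- A reader might infer that only the DSMS arm is clustered and that One Hope has no fixed groups. Section 2.2 describes shared appointments and classes there without saying whether membership is stable. Clustering at One Hope would enlarge the error, so a remedy confined to DSMS is too narrow.
- A reader might take 12 study patients per class as the worst case. That counts enrollees, while the power rests on completers.
- A reader might compare PAM-13 power at alpha 0.025 with the stated 85%. Independence already gives 90.4% there, so that comparison mixes clustering with the separate inconsistency in alpha.
- A reader might treat the class as the whole DSMS intervention. Section 2.2 also lists individual follow-up, a customised plan and self-assessment forms.

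**Clustering is second-order here.** With one site per programme, site confounding is the larger uncertainty, and a class term does not touch it. That is true, but it does not make an understated standard error acceptable.

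**Conclusion.** The point holds as a conditional one. For any positive within-class correlation with more than one study patient per class, an analysis without a class term understates the standard error of the site difference, and the independence-based power is too high. The direction follows from the delivery format; the size rests on the assumed m and ICC.

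Over the range examined, the loss is small for DKQ, which stays above 90% at alpha 0.025. It matters more for PAM-13 and the secondary outcomes, which fall below 80% towards the upper end. Type I error at nominal 0.025 could reach about 0.042. Clustering at One Hope, or few classes, would lower power further. The documents do not support saying that the standard error is known to be wrong by a given amount. This should be corrected, but it does not invalidate the design.

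**What to change.** 1. Record a class cohort identifier for each CDE-UNMH patient and shared-appointment attendance by group for each One Hope patient. The programme should already hold the class information, since section 3.1 says new patients are sent a class schedule confirmation; none of the six REDCap instruments in section 9.2 is described as holding it.
2. Write out the DKQ and PAM-13 analysis models and list the random effects of the A1c, BMI and PHQ-9 models. In all five, add a random intercept for class in the DSMS arm, plus a group term for One Hope if its groups prove stable. Alternatively, use a cluster-robust variance. Use small-sample degrees of freedom or an equivalent correction either way.
3. Restate power over a declared range of class size and ICC, at one reconciled primary alpha.

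The cost is one extra data field per patient (attendance by group at One Hope) and slightly wider intervals. If the ICC is near zero, little is lost. The confounding of programme with site needs separate treatment.
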